4.10.2 Nivolumab

Duration and compliance of the Nivolumab exposure will be assessed by computing the following variables:

- Number of cycles and number of doses per patient
- Nivolumab Duration of treatment (weeks) = (Date of last dose – Date of first dose + 28) / 7
- Cumulative dose (mg) = Sum of all doses administered
- Nivolumab RDI (%) = [(Cumulative dose received (mg) * 4 (weeks)) / (Nivolumab Duration of treatment (weeks) * 480 (mg))] * 100
- Number of patients with dose interruption and reasons for interruption
- Number of patients with dose delay and reasons for delay

Duration of the Nivolumab duration, and Cumulative dose will be summarized as continuous variables. RDI will be summarized as continuous variable and by categories:] - ; 60%[, [60% ; 75%[, [75% ; 90%[, [90% ; 100%],] 100% ; +].

The number of patients who had dose reduction/delay will be summarized by categories: (Any, 1, 2, 3+ times).

Another summary will be produced excluding treatment cycles after the progression for the patients that remain on treatment despite PD.

4.11 Efficacy Evaluation

4.11.1 Analysis and Data Conventions

The statistical hypotheses for testing the activity of monotherapy and the combination independently are:

$$H_0: p \leq p_0$$

$$H_1: p \geq p_1$$

Where H_0 is the null hypothesis, p is the observed response rate, p_0 is the response rate for available treatment options – **[REDACTED]**, H_1 is the alternative hypothesis and p_1 is the target response rate – **[REDACTED]**. For RXC004 monotherapy the primary summary measure is the DCR and the corresponding p_0 and p_1 are **[REDACTED]%** and **[REDACTED]%**. For the combination of RXC004 and nivolumab the primary summary measure is the ORR and the corresponding p_0 and p_1 are **[REDACTED]%** and **[REDACTED]%**.

4.11.1.1 Multi-centre Studies

There will not be any adjustment for study centres, subgroup analysis based on study centres are not planned.

4.11.1.2 Adjustments for Covariates

No statistical model will be provided for the analysis of study endpoints.

4.11.1.3 Handling of Dropouts or Missing Data

Missing data will not be imputed.

4.11.1.4 Multiple Comparisons/Multiplicity

Not applicable in this study.

4.11.1.5 Interim Analyses

There is no formal interim analysis planned

4.11.1.6 Examination of Subgroups

Not applicable in this study.

4.11.2 Primary Efficacy Variable(s)

All primary efficacy analyses will be conducted on the evaluable set.

Primary objective of study will consider the overall tumour response provided by Investigators. A listing containing information on target, non-target lesions, new lesions, overall response will be provided (ordered by arm, patient and visit).

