### **9.4.2 Efficacy**

#### **9.4.2.1 Primary Endpoint(s)**

The primary endpoint for the monotherapy arm is disease control rate and the primary endpoint for the combination arm is the objective response rate, both based on a individuals best overall response using investigator RECIST 1.1 assessments.

Objective response rate is defined as the proportion of subjects with a best overall response of complete response or partial response, based on local investigator assessment, as defined in RECIST 1.1. Confirmation of response is required for declaring PR or CR as the BOR. A confirmed response is defined as a CR or PR followed by a CR or PR a least 4 weeks later. The ORR will be summarised with accompanying 90% confidence interval calculated using the Clopper Pearson method. This will be calculated on the full analysis set and the evaluable analysis set with the evaluable analysis set calculation being considered primary. In the summary tables the incidence of unconfirmed responses will be presented as well as the patients with confirmed responses.

Disease control rate (DCR) is defined as the proportion of patients with a BOR of either CR, PR or stable disease (SD) for at least 16 weeks post baseline (corresponding to SD for 2 scheduled scans post baseline). A time window of 1 week around the week 16 visit will be applied. The DCR and associated 90% confidence interval, calculated using the Clopper Pearson method will be presented. This will be calculated on the full analysis set and the evaluable analysis set with the evaluable analysis set calculation being considered primary.

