4.2.6 Data summaries

Summaries will be presented as follows:

- Arm A and arm B in the same table, as detailed described in the following sections. A separate set of tables and figures on selected endpoints will be done for arm A1 and/or arm A2.
- No formal comparisons will be performed between arms.

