4.2.9 Analysis Conventions

Continuous data will be summarized in terms of the mean, standard deviation, median, minimum, maximum and number of observations, unless otherwise stated.

The minimum and maximum will be reported to the same number of decimal places as the raw data recorded in the database. The mean and median, will be reported to one more decimal place than the raw data recorded in the database. The standard deviation will be reported to two more decimal places than the raw data recorded in the database. In general, the maximum number of decimal places reported shall be four for any summary statistic.

Categorical data will be summarized in terms of the number of patients providing data at the relevant time point (n), frequency counts and percentages. Any planned collapsing of categories will be detailed in the SAP text and the data displays.

Percentages will be presented to one decimal place. Percentages will not be presented for zero counts. Percentages will be calculated using n as the denominator.

Changes from baseline in categorical data will be summarized using shift tables where appropriate.

Confidence intervals will be presented to one more decimal place than the raw data.

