4.11.2.1 Disease Control Rate (DCR)

The definition of DCR is provided in Section 3.2.1.3. DCR will be based on a individuals BOR using investigator RECIST 1.1 assessment. DCR is set as primary efficacy endpoint for arm A and secondary efficacy endpoint for arm B.

DCR and associated 90% confidence intervals (CIs), calculated using the Clopper Pearson method, will be summarized for arm A and arm B. For arm A, the patients who switched due to progression at first scan will be considered as having progressed. In addition, DCR will be summarized for arm A2 patients.

DCR will be listed for all patients in the evaluable set.

As an additional analysis, this analysis will be repeated considering the definition detailed in section 3.2.1.3.

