4.11.2.2 Objective Response Rate (ORR)

Definition of ORR is provided in Section 3.2.1.3. ORR will be based on a individuals BOR using investigator RECIST 1.1 assessment. ORR is set as primary efficacy endpoint for arm B and secondary efficacy endpoint for arm A.

ORR and associated 90% CIs, calculated using the Clopper Pearson method, will be summarized for arm A and arm B. For arm A, the patients who switched due to progression at first scan will be considered as having progressed. In addition, ORR will be summarized for arm A2 patients.

BOR will be listed for all patients in the evaluable set

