4.11.3 Secondary Efficacy Variables

All secondary efficacy analyses will be conducted on the FAS and, where appropriate, on the evaluable set.

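### As written, the SAP plans Arm A DCR and Arm B ORR on the evaluable set alone; the protocol also requires both on the full analysis set

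*SAP*

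**What the plan says.** Protocol 9.4.2.1 has a paragraph on ORR and one on DCR. Each asks for a 90% Clopper-Pearson interval and each contains the same instruction: "This will be calculated on the full analysis set and the evaluable analysis set with the evaluable analysis set calculation being considered primary".

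SAP 4.11.2 reads: "All primary efficacy analyses will be conducted on the evaluable set". The subsections below it follow suit. SAP 4.11.2.1 ends with "DCR will be listed for all patients in the evaluable set", and SAP 4.11.2.2 with "BOR will be listed for all patients in the evaluable set". Neither mentions the FAS. The FAS appears in SAP 4.11.3: "All secondary efficacy analyses will be conducted on the FAS and, where appropriate, on the evaluable set".

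SAP 4.11.2.1 and 4.11.2.2 also fix the status of each measure by arm. DCR is primary in Arm A and secondary in Arm B; ORR is primary in Arm B and secondary in Arm A.

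SAP 4.15, the section for changes from the protocol, says that the evaluable set now needs 4 weeks or more of RXC004 and a post-dose scan, or progression or death before the first scan, where a single dose was planned before. The stated purpose is to stop early dropouts unrelated to the drug from influencing the efficacy assessment. The formal definition is redacted in protocol Table 18 and SAP 4.5.

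**The concern.** DCR and ORR guide the go/no-go decision (SAP 4.14). The primary denominator excludes some treated patients, and the SAP revision history lists its definition as revised in version 3.0 (21 September 2023) and again in version 4.0 (24 May 2024), in an open-label study. The protocol's own safeguard is to show the same rates on all treated patients. If the patients removed by the 4-week rule would have counted as failures, the evaluable-set rate exceeds the FAS rate. Without the FAS result, the size of that gap does not appear in any planned table.

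The rule as worded in 4.15 also does not match its stated aim. A patient who stops RXC004 for toxicity before 4 weeks, without progressing or dying, is excluded although that dropout is due to the drug.

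**Working it through.** **1. Which set is planned for which result**

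| Result | Status | Protocol 9.4.2.1 | SAP |
|---|---|---|---|
| Arm A DCR | primary | FAS and evaluable | evaluable (4.11.2) |
| Arm B ORR | primary | FAS and evaluable | evaluable (4.11.2) |
| Arm A ORR | secondary | FAS and evaluable | FAS and, where appropriate, evaluable (4.11.3) |
| Arm B DCR | secondary | FAS and evaluable | FAS and, where appropriate, evaluable (4.11.3) |

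Because the analysis set follows primary or secondary status, the SAP gives a FAS rate to the two secondary results and not to the two primary ones.

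**2. Does the shared-table rule close the gap?** SAP 4.2.6 presents "Arm A and arm B in the same table, as detailed described in the following sections", and SAP 6.2 lists Arm A/B for both measures. Neither names an analysis set. A FAS table of DCR built for Arm B might carry Arm A as well, but nothing says so.

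**3. What would the FAS denominator be?** SAP 4.2.9 defines n as patients with data at the time point and adds: "Percentages will be calculated using n as the denominator". SAP 4.11.1.3 rules out imputation. No rule says how a treated patient with no evaluable post-baseline assessment counts, so such patients could drop out even of a FAS percentage.

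**4. How far could the rates differ?** The plan's power figure for 20 evaluable patients cannot be reproduced, because p0, p1, power and error level are redacted. The following is therefore an illustration only.

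- From the documents: about 20 evaluable patients per arm (SAP 4.14); two-sided 90% Clopper-Pearson intervals.
- Assumed: 10 patients with disease control or 3 responders; k = 0, 2 or 5 excluded patients, all failures.
- Rate = x/(20 + k). With n = 20 + k, the lower limit is the 0.05 quantile of Beta(x, n − x + 1) and the upper limit is the 0.95 quantile of Beta(x + 1, n − x).

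| k | DCR, x = 10 | ORR, x = 3 |
|---|---|---|
| 0 | 10/20 = 50.0% (30.2 to 69.8) | 3/20 = 15.0% (4.2 to 34.4) |
| 2 | 10/22 = 45.5% (27.1 to 64.7) | 3/22 = 13.6% (3.8 to 31.6) |
| 5 | 10/25 = 40.0% (23.6 to 58.3) | 3/25 = 12.0% (3.4 to 28.2) |

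For k = 5 the drop is 50.0 − 40.0 = 10.0 points in DCR and 15.0 − 12.0 = 3.0 points in ORR.

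**5. Do the Phase 1 data fix k?** No.

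- At 2 mg monotherapy, 0 of 6 stopped for a treatment-emergent event (protocol Table 5). The 90% upper limit is 1 − 0.05^(1/6) = 39.3%.
- At 1.5 mg with nivolumab, 2 of 8 stopped before the end of Cycle 1, cause not given (Table 8, footnote e).
- At the same dose, 2 of 8 stopped RXC004 for a treatment-emergent event, timing not given (Table 9): 25% (4.6 to 60.0). Whether these are the same two patients is not stated.

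**The case against.** The strongest reply is that silence is not deletion. SAP 4.11.2 does not use the word only, its choice agrees with the protocol's ranking of the evaluable set as primary, and SAP section 1 takes protocol version 7.0 as its basis. On that view the FAS analysis is still in force, and the shared-table rule would bring Arm A DCR and Arm B ORR into the FAS tables anyway. That reading is possible, but it is an inference. SAP 4.11.3 names the FAS where 4.11.2 does not, the DCR and BOR listings are confined to the evaluable set, and a programmer working from the SAP would have no instruction to produce the two FAS results.

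On the denominator, the n convention is general, DCR and ORR are defined as proportions of patients, and BOR has a not-evaluable category that counts as neither response nor control. This lowers the risk but does not settle the patient with no scan at all, so that part is an ambiguity and not a demonstrated error.

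Other outputs help: FAS waterfall and spider plots marked with BOR, a FAS listing of PFS, the swimmer plots, and a count of the evaluable set as a percentage of the FAS. A reader could rebuild approximate counts from them, but none is a planned rate with its 90% interval.

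The limits on size stand in full. The counts above are assumed, the illustrated intervals overlap heavily, the decision also rests on the totality of the data, and no effect on it can be shown. It is also fair that restoring the protocol's requirement needs only one sentence; the wider listings and the exclusion table are useful additions.

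**Conclusion.** The SAP departs from protocol 9.4.2.1 on both primary endpoints, and no readable text declares it. Followed as written, it yields no FAS rate or 90% interval for Arm A DCR or Arm B ORR. This rests on legible text and does not depend on the redacted evaluable-set definition, with one reservation: a redacted bullet in SAP 4.15 could mention the change.

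The point about early toxicity dropouts is weaker. It rests on a single sentence in SAP 4.15 in which the and/or is not bracketed, so it is unclear whether patients who progress or die before the first scan also need 4 weeks of RXC004.

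The numerical effect is unknown. With no exclusions the two rates agree; with 2 to 5 excluded failures the illustrated DCR falls by 4.5 to 10.0 points and the ORR by 1.4 to 3.0 points. The evaluable set may properly stay primary. The plan should be corrected because the missing analysis is the protocol's direct check on a denominator that the SAP has since narrowed.

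**What to change.** - **SAP 4.11.2:** add DCR and ORR with 90% Clopper-Pearson intervals on the FAS for both arms, shown beside the evaluable-set results, which remain primary. State that a patient with no evaluable post-baseline assessment counts as a non-responder and as not having disease control, so that the denominator is every FAS patient in the arm. This is the essential change.
- **Listings:** extend the DCR and BOR listings to the FAS.
- **Exclusions:** tabulate exclusions from the evaluable set by arm and reason. SAP 4.4.2 already covers major deviations leading to exclusion; other reasons, including early stopping, need adding.
- **SAP 4.15, evaluable-set rule:** bracket the and/or, and reconcile the rule with its stated aim.
- **SAP 4.15, declaration:** declare and justify any departure from protocol 9.4.2.1 that remains.

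The cost is SAP wording, two repeated tables, two extended listings and one exclusion table. The primary set, the sample size and data collection do not change.

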4.11.2.1 Disease Control Rate (DCR)

The definition of DCR is provided in Section 3.2.1.3. DCR will be based on a individuals BOR using investigator RECIST 1.1 assessment. DCR is set as primary efficacy endpoint for arm A and secondary efficacy endpoint for arm B.

DCR and associated 90% confidence intervals (CIs), calculated using the Clopper Pearson method, will be summarized for arm A and arm B. For arm A, the patients who switched due to progression at first scan will be considered as having progressed. In addition, DCR will be summarized for arm A2 patients.

DCR will be listed for all patients in the evaluable set.

As an additional analysis, this analysis will be repeated considering the definition detailed in section 3.2.1.3.

4.11.2.2 Objective Response Rate (ORR)

Definition of ORR is provided in Section 3.2.1.3. ORR will be based on a individuals BOR using investigator RECIST 1.1 assessment. ORR is set as primary efficacy endpoint for arm B and secondary efficacy endpoint for arm A.

ORR and associated 90% CIs, calculated using the Clopper Pearson method, will be summarized for arm A and arm B. For arm A, the patients who switched due to progression at first scan will be considered as having progressed. In addition, ORR will be summarized for arm A2 patients.

BOR will be listed for all patients in the evaluable set

4.11.3 Secondary Efficacy Variables

All secondary efficacy analyses will be conducted on the FAS and, where appropriate, on the evaluable set.

4.11.3.1 Percentage change in sum of target lesions

The % change in sum of target lesions is defined in Section [3.2.1.4](#) .

Percentage change in tumour size will be derived at each visit by the percentage change from baseline in the sum of diameters of target lesions will be provided for arm A and arm B. It will also be summarized for arm A2.

In arm A and arm B, % change in sum of target lesions will be always computed considering screening sum of diameters as baseline. For patients in cluster arm A2, % change in sum of target lesion will be computed considering as reference the sum of diameters computed at Week 8. In case some individual lesions are not measured, the whole sum of target lesions will be considered as missing.

Percentage change in tumour size will be listed per visit for all patients in FAS.

The best percentage change in tumour size will be the patients value representing the largest decrease (or smallest increase) from baseline in tumour size.

A waterfall-plot will be produced to report the best % change in sum of target lesions for each patient (considering the minimum observed value) ordered by largest increase to greatest decrease. In addition, two waterfall-plot will be produced to report the % change in sum of target lesions at Week 8 and Week 16. Best overall responses (BOR) will be highlighted for each patient. The figure will be repeated considering RNF43 and RSPO2/3 Status instead of BOR.

A Spider-plot will be drawn to describe the % change in sum of target lesion. Vertical axis will represent the % change in sum of target lesions (% change in tumour size) while the horizontal axis will represent days from screening, as follows:

day (x-axis) = date of RECIST 1.1 assessment – first dose of study treatment (C0D1)

Best overall responses (BOR) will be highlighted for each patient. The figure will be repeated considering RNF43 and RSPO2/3 Status instead of BOR.

All plots will be provided for the FAS separately for arm A, arm A2 and arm B. The spider plot for A2 will still use the original baseline to week 8 so it is clear what the changes were when the patient switched to the combination.

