Disease Control Rate (DCR; defined as CR+ PR+ durable stable disease lasting for at least 16 weeks) was selected as the primary endpoint for the RXC004 monotherapy arm because it considers both tumour shrinkage and durable disease stabilisation. It is possible and more likely that RXC004 efficacy could result in prolonged stable disease rather than tumour shrinkage. As complete ablation of tumour cell proliferation has been observed in preclinical models, this mechanism of action could still lead to patient benefit, increased progression free survival and ultimately an overall survival benefit for the patient.

For this endpoint, a value of **CCI**% DCR will be used as a reference, as this was consistently reported in the studies of TAS-102 and regorafenib in a similar but unselected patient population (Grothey et al 2013 and Mayer et al 2015) and an improvement over this value would be considered relevant, firstly because the DCR rate in the reported studies was based on SD at **CCI** weeks, whereas in this study at least 16 weeks of SD is required, and secondly because of the preliminary evidence that RNF43 mutated MSS CRC may have a poorer prognosis than the general MSS CRC population.

However, acknowledging that Disease Control Rate is difficult to interpret in a single arm study, the secondary endpoints of the study include the best % change in the sum of target lesions from baseline, the ORR (monotherapy) and duration of response (DoR) according to

RECIST 1.1, as well as PFS and OS. All of these endpoints will be taken into account when determining whether RXC004 has demonstrated sufficient clinical activity to support further clinical development as a monotherapy. Further details are provided in sections 9.2 and 9.4.

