3.2.1.4 Percentage change in the sum of target lesions

Percentage change in sum of diameters of target lesions from baseline for patients with measurable disease, will be calculated for each RECIST assessment visit, as follows:

Percentage change in the sum of target lesions (%) = $(\Sigma \text{ observed value after baseline} - \Sigma \text{ observed value at baseline}) * 100 / \Sigma \text{ observed value at baseline}$

Percentage change in sum of diameters of target lesions was set as a secondary efficacy endpoint for both arm A and arm B.

The best overall percentage change in the sum of target lesions (%), representing the largest decrease (or smallest increase in the absence of a decrease) from baseline, will also be considered as an efficacy endpoint.

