4.2.3 Definition of Baseline and Post-baseline Assessments

A baseline assessment will be defined as the last assessment performed prior to the first dose of study treatment (C0D1). While many of these assessments will be performed on the day of the first dose, others will be performed during screening. If a patient is missing an assessment typically performed on the day of the first dose, screening values may be substituted as baseline.

Patients treated with RXC004 monotherapy (arm A) that radiologically progress as per RECIST1.1 at the first 'on treatment' scan, may be treated with RXC004 + Nivolumab combination. Accordingly, the following groups of analyses have to be defined to clarify which patients and which information in arm A will be utilized:

- **Arm A (RXC004 monotherapy):** this group will include information for all patients enrolled in arm A.
- **Arm A1 (RXC004 monotherapy):** this group will include information of all patients enrolled in Arm A who were on monotherapy throughout the study - ie. subjects who did not radiologically progressed at the first scan (week 8) or who radiologically progressed

at the first scan (week 8) but remained on monotherapy or who withdrew before the first scan.

- **Arm A2 (RXC004 + Nivolumab):** this group will include information of patients enrolled in arm A who radiologically progressed at the first scan (Week 8) and then switch to receive combination therapy of RXC004 + Nivolumab either at Week 8 or later. The last scan before the switch to combination treatment will be set as the arm A2 baseline RECIST1.1 scan for the combination treatment. The date of the last scan before switching to combination treatment will also be used to determine the arm A2 baseline date for all the efficacy endpoints except OS. OS will keep the same baseline regardless of the progression. For assessments other than efficacy, Arm A2 summaries, will include data from start of monotherapy until end of combination treatment.
- **Arm B (RXC004 + Nivolumab):** this group will include information on all patients enrolled in arm B.

Some patients with symptomatically stable disease may continue treatment after the initial RECIST 1.1 - defined progression, until symptomatic/clinical progression or a second RECIST 1.1 PD assessment (relative to the initial RECIST1.1 progression, for a given study treatment).

Change from baseline is derived where both baseline and post-baseline values are available:

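### Arm A percentage change in target lesions has no cut at the switch, so scans taken on RXC004 + nivolumab can enter the monotherapy best-change waterfall and spider plot

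*SAP*

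**What the plan says.** SAP 4.2.3 defines the Arm A group, labelled RXC004 monotherapy, by its members: "this group will include information for all patients enrolled in arm A". Patients who later switch are therefore in it. No end date for their data is given.

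On the reference value, SAP 4.11.3.1 says "In arm A and arm B, % change in sum of target lesions will be always computed considering screening sum of diameters as baseline". On best change it says "A waterfall-plot will be produced to report the best % change in sum of target lesions for each patient (considering the minimum observed value", and SAP 3.2.1.4 describes the same quantity as "representing the largest decrease (or smallest increase in the absence of a decrease) from baseline, will also be considered as an efficacy endpoint". For fixed times, "two waterfall-plot will be produced to report the % change in sum of target lesions at Week 8 and Week 16". The spider plot places each scan by days since the first dose on C0D1. Plots are produced for Arms A, A2 and B. Arm A1, which leaves switchers out, is not used for this endpoint (SAP 4.11.3.1 and 6.2).

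For DCR in Arm A, by contrast, "the patients who switched due to progression at first scan will be considered as having progressed". The same sentence stands under ORR (SAP 4.11.2.2) and PFS (SAP 4.11.3.2), and BOR runs only to progression or death (SAP 3.2.1.1).

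Protocol 4.3.1 concedes that DCR is hard to interpret in a single arm and lists best percentage change among the supporting secondary endpoints: "All of these endpoints will be taken into account when determining whether RXC004 has demonstrated sufficient clinical activity".

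**The concern.** The plan recognises for three endpoints that an Arm A result must not absorb what happens after nivolumab is added. The tumour-size section has no equivalent rule. A programmer following it literally would carry a switcher's later scans, still measured from screening, into figures headed as monotherapy.

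For best change the effect has one direction. Adding scans to a minimum can lower it or leave it alone, but never raise it. The added scans are taken on a second active agent. The resulting figure informs the decision whether RXC004 alone is active enough to develop further.

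**Working it through.** The plan gives no figure to reproduce, and no power or alpha value bears on this point. The check is a reading of the rules followed by simple arithmetic.

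**1. Is there a cut for Arm A?**

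| Endpoint | Rule that keeps post-switch data out of Arm A |
|---|---|
| BOR | Runs to progression or death (SAP 3.2.1.1) |
| DCR, ORR, PFS | Switchers count as progressed (SAP 4.11.2.1, 4.11.2.2, 4.11.3.2) |
| Percentage and best percentage change | None in SAP 3.2.1.4, SAP 4.11.3.1 or Protocol 9.4.2.2 |

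**2. Do post-switch scans exist?** Yes. Protocol Table 1 continues 8-weekly scanning through the combination phase, timed from the first dose of IP. Footnote j allows up to 20 patients to switch.

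**3. Which outputs are exposed?**
- *Best-change waterfall and spider plot:* exposed. One takes a minimum with no end date. The other runs from C0D1 with no end date.
- *Week 8 waterfall:* not exposed, because that scan precedes the switch.
- *Week 16 waterfall and by-visit summaries:* unclear. Protocol 5.1 criterion 12 has the combination start within 28 days of the Week 8 (+/- 1) scan, or of a later scan for those who stayed on monotherapy. For a patient switching on the Week 8 scan, time on combination at the Week 16 (+/- 1) scan runs from 15 - (9 + 4) = 2 weeks to 17 - 7 = 10 weeks. SAP 4.2.1 restarts the day count at the first combination dose, so that scan may not be labelled Week 16 at all.

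**4. How far can a bar move?** Let w be the change from screening at the last monotherapy scan, assumed to be the patient's lowest monotherapy value. Let s be the further shrinkage on combination, measured from that scan.

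Arm A value without a cut = (1 + w) x (1 - s) - 1. With a cut it stays at w.

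For w = 20% and s = 30%: 1.20 x 0.70 - 1 = -16%.

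| w | s = 10% | s = 30% | s = 50% | With cut |
|---|---|---|---|---|
| 0% (progression by new or non-target lesion) | -10% | -30% | -50% | 0% |
| +20% | +8% | -16% | -40% | +20% |
| +40% | +26% | -2% | -30% | +40% |
| +60% | +44% | +12% | -20% | +60% |

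From +20%, the bar goes below zero once s exceeds 1 - 1/1.20 = 16.7%. It reaches -30% at s = 1 - 0.70/1.20 = 41.7%.

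**5. Effect on the arm.** One patient moved from +20% to -16% shifts the mean best change of 20 patients by 36/20 = 1.8 points. Four such patients shift it by 7.2 points. All values of w and s, and the number of patients, are assumptions.

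**The case against.** The strongest reply is that a silence is being read as an instruction. The Arm A definition says who is included, not over what period. The word *always* fixes the reference value, not the data window. SAP 4.2.3 resets the A2 baseline at the switch for efficacy endpoints other than OS, and SAP 4.2.1 restarts the day count, so a split may well have been intended. SAP 4.11.3.1 also makes a point of keeping the original baseline to Week 8 in the A2 spider plot, which would be largely redundant if the Arm A plot already showed whole trajectories. The endpoint is secondary and descriptive. Listings flag switchers, the swimmer plot colours the two phases, and BOR highlighting would expose a progressor with a negative bar.

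Much of this stands. The SAP nowhere says outright that post-switch scans belong to Arm A. But none of these features takes them out of the Arm A best-change or spider outputs. The A2 outputs show switchers a second time without removing them from Arm A.

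Three stronger readings are tempting and are not supported:
- *A switcher's Week 16 value in the Arm A plot is always an on-nivolumab value.* The restarted day count leaves this open.
- *Every affected output is biased in favour of RXC004.* Only best change has a fixed direction. Switchers have already progressed, and their later by-visit values could be unfavourable.
- *A 30% shrinkage on combination appears as -30%.* It starts from an enlarged sum. From +25% it gives 1.25 x 0.70 - 1 = -12.5%, and reaching -30% needs 1 - 0.70/1.25 = 44%.

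**Conclusion.** The point holds for the Arm A best-change waterfall and spider plot: followed as written, the SAP lets scans on RXC004 + nivolumab into outputs headed as monotherapy. For the Week 16 waterfall and by-visit summaries, the finding is only that two programmers could reasonably produce different results, with an effect in either direction.

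A reader might infer that the primary monotherapy result is contaminated. It is not, because DCR, ORR and PFS have their own switcher rule.

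The size cannot be fixed from the documents. It depends on how many patients switch and how far their sums fall. Switching requires progression at the Week 8 scan, eligibility for Arm B, Sponsor approval and an open combination phase. A best-change bar moves only if the sum on combination falls below the patient's lowest monotherapy value. The plan should still be corrected, because Protocol 4.3.1 uses this endpoint in judging monotherapy activity and the correction is cheap.

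**What to change.** Add to SAP 4.11.3.1: *For Arm A, percentage change, best percentage change, and all waterfall and spider plots use only scans up to and including the last scan before the first combination dose. Later scans are presented under Arm A2 only.*

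That scan is already the A2 baseline in SAP 4.2.3, so no new date has to be derived. SAP 4.11.3.1 currently names Week 8 as the A2 reference, which can be an earlier scan in a patient who stayed on monotherapy after progression. The two sections should be aligned at the same time. The proposed cut is not identical to the rule for DCR, ORR and PFS, which stop at progression. It keeps monotherapy scans taken after progression, which are still monotherapy data.

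The cost is one sentence and one date filter, with no new data. The small downside is that Arm A outputs at Week 16 and later lose patients who progressed and switched, which enriches them for non-progressors. Each such output should state how many patients are absent for that reason.
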